7.4 Duration of therapy and Study Period

Treatment with tTF-NGR may continue until one of the following criteria applies:

disease progression

- intercurrent illness that prevents further administration of treatment according to the judgement of the Investigators
- ➤ Occurrence of Dose Limiting Toxicity (DLT), i.e., unacceptable adverse event(s), including Grade ≥ 3 (CTCAE) toxicity for any organ with the exception of the hematopoietic system or Grade 4 for the hematopoietic system attributed to the IMP
- patient decides to withdraw from the study
- general or specific changes in the patient's condition rendering the patient unfit for further treatment in the judgement of the Investigators
- patient is lost to follow-up
- death

Duration of Study Period with follow-up is defined as being

- > from day of signature of Informed Consent to
- day 5 after the start of the last dose level plus 3 months of observation

Patients will be removed from study treatment when any of the criteria listed under section 7.4 applies or the Study Period is completed.

In patients with objective response and good toleration on a specific dose-level reached, or with stable disease upon 8 cycles of therapy, individual dose-escalation will be stopped and patients will be further treated for up to 3 months with the specific dose under which response occurred, or in case of stable disease with the dose at the 8th cycle. If this patient is treated with dose-escalation steps, he/she will be replaced by the next patient to continue the dose-escalation. This is to not add further risk to an individual, when individual benefit is visible. Upon this time Study Period in these individual patients will end. These patients will be eligible for further compassionate-use treatment with the IMP on the dose-level after completion of the Study Period as long as they benefit from treatment in accordance with §34 of the Declaration of Helsinki (2013 Fortaleza, Brazil). Serious adverse events (see paragraph 13 of this protocol) occurring during compassionate use treatment will be reported as within the defined Study Period to guarantee patient safety within this trial.

8. Dosing delays and dose de-escalations in individual patients

De-escalation in individual patients in dosing is not allowed during the Study Period to not interfere with the description of Dose Limiting Toxicity (DLT) and MTD.

Delays in dosing of the next application for up to 6 days in individual patients are allowed in case anticipated adverse events connected with the composition of the drug or the mechanism of action of tTF-NGR occur, which need to be addressed before treatment can continue. This is in particular foreseen in the following situations:

- 1. Consumption of platelets due to tumor vascular coagulation with platelet count drops to grade 3 of CTCAE version 4.0 (page 112; 25.000 50.000 platelets per microliter) to allow recovery of counts to >50.000 per microliter,
- 2. Infusional reactions due to the protein application in case tTF-NGR was applied without premedication (see below) to allow resolution to CTCAE grade <2 and a following application with premedication.

However, in patients with objective response and good toleration of the drug, who are further treated in the compassionate-use program with the IMP after completion of the Study Period, dosing delays and/or modifications are allowed and handled according to the judgement of the Investigators.

9. Dose Limiting Toxicity (DLT) and Maximum Tolerated Dose (MTD)

Dose Limiting Toxicity (DLT): DLT is defined as occurrence of toxicity of Grade 3 or more according to the revised NCI Common Terminology Criteria for Adverse Events (CTCAE) version 4.0 (http://ctep.cancer.gov) for non-hematological toxicity or Grade 4 or more for hematological toxicity. DLT must be considered by the investigator as being causally related to the IMP. In case the investigator comes to no decision, the data safety monitoring board is to be involved. Intensity of toxicity will be graded according to CTCAE using a five-point scale:

α	
C	L

Grade	Equivalent To:	Definition
Grade 1	Mild	Mild; asymptomatic or mild symptoms; clinical or diagnostic observations only; intervention not indicated.
Grade 2	Moderate	Moderate; minimal, local or noninvasive intervention indicated; limiting age-appropriate instrumental Activities of Daily Living (ADL).
Grade 3	Severe	Severe or medically significant but not immediately life-threatening; hospitalization or prolongation of hospitalization indicated; disabling; limiting self care ADL.
Grade 4	Lifethreatening/Disabling	Life-threatening consequences; urgent intervention indicated
Grade 5	Death	Death related to AE.

When DLT is observed in the 1st patient, up to 5 more patients will be treated on the same dose level, or in case of deadly DLT in the dose level below (verification group for DLT; maximum of 6 patients on this level). Upon observation of no additional DLT after treating 6 patients on this dose level dose escalation can be resumed in one patient. The remaining 5 patients can be treated without dose-escalation until tumor progression or DLT. Upon observation of one more episode of any DLT within the verification group, patient accrual to this verification group is stopped with this second patient with DLT and de-escalation by a $0.5 \text{ mg/m}^2/\text{day}$ step is performed in 5 further patients until $\leq 1 \text{ DLT}$ occurs in 5 further patients treated on a specific dose-level, i.e. with $\leq 1/6$ patients in total with DLT on this dose level (scheme see below).

Maximum Tolerated Dose (MTD): MTD is the dose below the lowest dose level on which reproducible episodes of any DLT are observed. Reproducible episodes of DLT have also to be stated if DLT occurs in different organ systems of individual patients.

[figure not shown]
10. Dose escalation and de-escalation according to toxicity and dose recommended for phase II trials (RDPII)

The patients will be treated daily with tTF-NGR by 1-hour iv infusions for 5 days with MRI studies before, 4-6 hours after the 1st application, and on day 5 after treatment as decided by the Investigator.

[figure not shown]
Starting dose will be 1 mg/m²/day. Intraindividual dose-escalation will be performed in 1 patient in 0.5 mg/m²/day steps (to a maximum of 8 cycles) upon a rest period of 16 days for the next treatment cycle of 5 days. The maximum number of 8 dose escalations is reached only if stable disease (SD) is ongoing upon 8 cycles of therapy. Dose-escalation is stopped before the maximum number of 8 escalation steps if tumor response, tumor progression or a Dose-Limiting Toxicity (DLT) is observed. If tumor response is observed or if a patient is diagnosed with progressive disease (PD) after ≥ 2 cycles or clinically as judged by the investigator even before 2 cycles, this patient will go off study and will be replaced by a further patient in whom individual dose escalation will be resumed, starting with the highest dose level reached without DLT in the previous patient. When any DLT is observed in this patient, intraindividual dose escalation is stopped and the patient is taken off study. In case of stable disease or response and resolution of the DLT this patient can be further treated on the highest tolerable dose level without DLT until any of the criteria under 7.4 is reached. This treatment will then be given on an individual compassionate-use basis (off study) according to § 34 of the Helsinki declaration (2013, Fortaleza; Post-Trial Provision).

If this first observed DLT is nonfatal, up to 5 more patients will then be treated on the same dose level having caused DLT (verification group). Patients of the verification group will be treated in sequence of each other, thus a patient has to tolerate the first cycle (5 days) and the rest period of 16 days without DLT before the next patient can be added to this verification group.

Upon observation of no additional DLT in the verification group in a minimum of 2 cycles for each patient, dose escalation can be resumed in one patient out of these until DLT (continue as above). The remaining patients in the verification group will be further treated at this dose-level until any of the criteria under 7.4 is reached.

Upon observation of one more episode of any DLT within the first 2 cycles given to the patients in the verification group, patient accrual to this verification group is stopped with this second patient with DLT and de-escalation by a $0.5 \text{ mg/m}^2/\text{day}$ step is performed in further up to 5 patients. If on the next lower dose level there are $\geq 2 \text{ DLT}$ in 5 further patients (i.e., $\geq 2 \text{ DLT}$ in 6 patients in total on this dose level), de-escalation will continue. In case, patients of the verification group experience DLT in a later cycle (3rd and following), this will be counted as DLT with all consequences, although the procedure of the study was not influenced before such an event occurred.

Dose de-escalation will continue until ≤1 DLT occurs in 5 further patients treated on a specific dose-level, i.e. there are ≤1/6 patients with DLT in total on this dose level. This dose level is declared the MTD and will be recommended for further studies, such as phase II trials (RDPII).

If an observed DLT is fatal, the above dose escalation scheme is modified. Denote this dose d_{fatal} . In the unlikely event that further patients are treated with this dose, treatment in these patients will be stopped at this dose level and the investigator decides how to go on with the treatment in these patients. The next patients will not be treated with the dose d_{fatal} , but on the next lower dose level d_{fatal} - 0.5 mg/m²/day. If on the dose level d_{fatal} - 0.5 mg/m²/day no DLT or not more than 1 DLT is observed that is non-fatal, further patients are treated on the dose level d_{fatal} until any further DLT is observed or 6 patients are included on this dose level in total. Possible later dose escalation to a level at which one death occurred has to be discussed with the data safety board.

Only in the very unlikely event, that DLT occurs at the starting dose or the dose 0.5 mg/m²/day higher, further dose de-escalation below the starting dose level can be performed as described to establish MTD.

The above procedure is constructed so that MTD is defined similarly to a standard 3+3 design. I.e., any dose with observed DLT in $\leq 1/6$ patients is defined to be the MTD, if on the next higher dose level the observed number of patients with DLT is $\geq 2/6$. The following summary visualizes this procedure:

```
Start 1 pt at 1 mg/m²/day with individual dose escalation at 0.5 mg/m²/day for 5 days every 3 weeks until any DLT (= dose "d1") or to a max of 8 cycles

Verification group (VG) of ≤5 further pts at d1 without indiv. dose esc.

(Verification group (VG) of ≤5 further pts at d1-0.5mg/m²/day without indiv. dose esc. in case a death occurs as DLT)

No further DLT in VG > resume dose escalation: start 1 pt of VG at d1 + 0.5 mg/m²/day (d), then as above

1 further DLT in VG > dose de-escalation d1 - 0.5 mg/m²/d, 5 further pts (d-1(-2))

>1 further DLT: d-1 = MTD

>1 further DLT > dose de-escalation, continue as above
```

Again, if a patient has been taken off the study due to a DLT or progressive disease, the patient may further be treated as follows. If the patient has stable disease or response and the DLT has been resolved, outside the study the patient may be treated

with the study medication on the highest tolerable dose level without DLT (§ 34 Declaration of Helsinki, Fortaleza 2013). In case of progressive disease or if the DLT has not been resolved, different treatment options are offered.

11. Study objectives and end-points

Primary Objectives

To evaluate the maximum tolerated dose (MTD) and the dose-limiting toxicity (DLT) of intravenously (i.v.) infused daily applications of tTF-NGR in patients with cancer (solid tumors and lymphomas), who had obtained all standard treatment known for their disease entity prior to entry on study.

Secondary Objectives

- 1. To determine the perfusion and vascular volume fraction of measurable tumor lesions versus normal reference tissue before and after tTF-NGR application by MRI as a imaging surrogate parameter for biological activity of the IMP.
- 2. To obtain pharmacokinetic data of tTF-NGR.

Primary Safety end-point

Maximum Tolerated Dose (MTD). MTD is the dose below the dose leading to reproducible episodes of Dose Limiting Toxicity (DLT) in at least 2/6 patients. DLT will be characterized by clinical, blood and serum monitoring at specified time points before and during study period.

Secondary Safety end-points

- 1. Occurrence and frequency of inhibition of tumor blood flow as measured by contrast-enhanced Magnetic Resonance Imaging (MRI).
- 2. Occurrence and frequency of tumor response defined as Complete Response (CR), Partial Response (PR), or Stabile Disease (SD) as defined by RECIST criteria.

Descriptive statistics will be used.

12. Patient evaluation and follow-up

Patients will be evaluated as outlined in the study calendar below. The time-points given are in relation to IMP application. Additional visits will occur as clinically indicated.

Study Calendar for each 5-day cycle

Days (d), hours (h), weeks (w) post IMP	pre (within 1 w)	at inf. stop	1 h	5 h	daily	5 d	weekly	repeat cycles (see left)	monthly from end of IMP application	study period end
History + examination	Х	Х	х	Х	Х	Х	х		х	х
Lab tests (FBC, biochemistry, coagulation)	х	Х	х	х	Х	х	Х		х	Х
Oxygen sats (- = continuous), ECG-monitoring	х	х-	х-	х-	Х	Х	х		х	Х
Investigator to check eligibility	х						х			
Informed consent	Х									
Clinical/blood assessment of AE and toxicity	х	Х	х	х	х	х	х		х	Х
Tumor measurements	х								X (without relation to IMP)	Х
MRI, vascular volume fraction*	Х			Х		Х				(x)
Pharmacokinetics	х	Х	X (see below)	Х	Х	х	х		х	
НАНА						Х				Х
CNS-MRI	х									

^{*,} times are selected by the decision of the investigator, patients in the verification groups are to be evaluated at least in one cycle of therapy

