14.1 Infusional reactions

Allergic reactions including rash, fever, rigors and bronchospasm are possible after infusion of proteins. This did not happen during the treatment of the first patients. However, in case these side effects occur, patients will be premedicated with chlorpheniramine, paracetamol and corticosteroids to prevent such reactions.

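### Section 8 item 2 allows on-study re-dosing after an infusional reaction and sets no upper grade, while Sections 7.4 and 9 make a related reaction of Grade 3 or higher a DLT that ends study treatment; nothing says which prevails.

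*Combined protocol and SAP*

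**What the plan says.** Five parts of the protocol bear on the same event.

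- **Section 8 (dosing delays).** The general rule is permissive: "Delays in dosing of the next application for up to 6 days in individual patients are allowed in case anticipated adverse events". Two situations are listed. Item 1 is "Consumption of platelets due to tumor vascular coagulation with platelet count drops to grade 3 of CTCAE version 4.0". Item 2 is "Infusional reactions due to the protein application in case tTF-NGR was applied without premedication (see below) to allow resolution to CTCAE grade <2", to be followed by dosing again: "and a following application with premedication". The same section rules out lowering an individual patient's dose during the Study Period.
- **Section 14.1.** Rash, fever, rigors and bronchospasm are listed as possible reactions, and "in case these side effects occur, patients will be premedicated with chlorpheniramine, paracetamol and corticosteroids". No grade is mentioned.
- **Section 9.** "DLT is defined as occurrence of toxicity of Grade 3 or more according to the revised NCI Common Terminology Criteria for Adverse Events" applies to non-haematological toxicity; the haematological threshold is Grade 4. The investigator must judge the event to be caused by the study drug.
- **Section 7.4.** "Treatment with tTF-NGR may continue until one of the following criteria applies"; one of those criteria is a DLT, with the same grade thresholds. A patient who meets any criterion is removed from study treatment.
- **Sections 3.5 and 10.** Section 3.5 allows more treatment after a DLT only if it has resolved in a responding patient. Section 10 takes the escalation patient off study at a DLT. With stable disease or response and a resolved DLT, it allows further dosing only outside the study, at a level without DLT.

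**The concern.** A severe infusional reaction after an unpremedicated infusion fits both the delay rule and the removal rule. One leads to another on-study infusion, the other to the end of study treatment.

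Two things are at stake. The first is the individual patient: two investigators following the same protocol could act differently after the same severe reaction. The second is the primary endpoint. The escalation scheme turns on single events. A first DLT opens a verification group, and one more DLT in that group stops its accrual and lowers the dose by one step. If a reader took Section 8 as an exception for anticipated infusional reactions, the classification of one event could change the path to the MTD.

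**Working it through.** **The plan's own figure.** Section 16.1 gives a minimum of 7 patients: 1 escalation patient with a DLT, 1 verification patient with a DLT, and 5 patients one step lower. 1 + 1 + 5 = 7, so the figure reproduces. This point does not alter it. The rest of the check is textual.

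**Step 1: does the event meet the DLT definition?** Three conditions are needed.
- Non-haematological: an infusional reaction such as bronchospasm is.
- Related to the drug: item 2 concerns reactions it already attributes to the protein.
- Grade 3 or more: item 2 neither requires nor excludes this.

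**Step 2: what each rule says by grade**, for a related reaction to an infusion given without premedication:

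| Grade | Section 8 item 2 | Sections 7.4 and 9 | Compatible? |
|---|---|---|---|
| 1 | Already below Grade 2, so nothing to wait for | Below the threshold | Yes |
| 2 | Delay allowed, then dose with premedication | Below the threshold | Yes |
| 3 or 4 | Within the wording: delay allowed, then dose with premedication | DLT; removed from study treatment | No |

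The recovery target (below Grade 2) implies that item 2 is meant for reactions of Grade 2 or higher. The overlap starts at Grade 3.

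**Step 3: compare the two items.** Item 1 is confined to Grade 3 platelet drops and the haematological DLT threshold is Grade 4. Since 3 < 4, item 1 cannot collide with the DLT rule. Item 2 has no such ceiling against a threshold of Grade 3.

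**Step 4: does another section resolve it?**
- Sections 7.4 and 9 contain no exemption for infusional reactions.
- Section 3.5's exception needs a responding patient; item 2 does not.
- Section 10's exception is off study and at a level without DLT. Item 2 is on study, and Section 8 forbids lowering the individual's dose, so the repeat infusion would not be at a lower level.
- No sentence states which section takes precedence.

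**Step 5: where one event enters the scheme.** Under Sections 9 and 10, a non-fatal DLT in the escalation patient ends that patient's escalation and opens a group of up to 5 more patients at the same dose. One further DLT in that group stops accrual and moves the next patients down by 0.5 mg/m²/day. Differing classification of a single event can therefore change whether a group opens, or whether the scheme steps down.

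**The case against.** The strongest reply is that there is no true contradiction. Section 8 only permits a delay, whereas Section 7.4 requires removal, and a permission does not override a requirement. Section 8 speaks of problems to be dealt with before treatment continues, so it presupposes that treatment may continue. The platelet item stops below its DLT threshold, and a recovery target below Grade 2 fits a Grade 2 reaction. On this reading item 2 covers only events below the DLT threshold. It is plausible, and may be what the authors intended. It does not close the point: item 1 states its limit and item 2 does not, and a specific provision for a named reaction can reasonably be read as an exception to a general rule.

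Three stronger inferences should not be drawn.
- A reader might infer that Section 8 makes the event count as no DLT. It does not say so. Section 9 alone defines a DLT, and Section 8 justifies its ban on individual de-escalation by the need to protect the description of DLT and MTD. The ambiguity about continued treatment is therefore firmer than the ambiguity about the count.
- A reader might want a probability that the two readings diverge. The documents give no rate of Grade 3 or higher infusional reactions, and Section 14.1 reports none in the first patients, so any such figure would rest on an unanchored assumption.
- A reader might infer that verification patients would be premedicated after an unpremedicated index reaction, so that the DLT is tested under different conditions. No section prescribes this; Section 14.1 can equally be read as premedicating only those who have reacted.

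**Conclusion.** The point holds in a limited form. For a drug-related infusional reaction of Grade 3 or higher after an unpremedicated infusion, the protocol supports two readings: removal under Sections 7.4 and 9, or delay and on-study re-dosing under Section 8 item 2. It states neither an exemption nor a precedence rule. Grade 2 reactions are not affected, and Section 8 permits re-dosing rather than requiring it.

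The firm consequence is that the handling of such a patient depends on the reader. The consequence for the MTD is conditional: it arises only if someone treats Section 8 as also removing the event from the DLT count, which the text does not say but does not expressly exclude. In that case one event can alter one step of the scheme. The sample-size statement is untouched. The conclusion rests on the wording alone and needs no assumed rate. It is worth correcting before use because it concerns an anticipated toxicity and a primary endpoint decided by single events.

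**What to change.** Reconcile Section 8 item 2 and Section 14.1 with Sections 7.4 and 9, and with the post-DLT provisions in Sections 3.5 and 10, so that an infusional reaction of Grade 3 or higher has:

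1. one stated consequence for continued study treatment; and
2. one stated classification in the DLT count that determines the MTD.

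Which clinical rule applies is for the sponsor to decide; the need is that all six sections give the same answer. An explicit grade range in item 2, as item 1 already has, or a sentence stating which section takes precedence, would remove the ambiguity.

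The cost is amendment wording and cross-references. No patients, visits, procedures or analyses are added. If the change is judged substantial, Section 22 requires a favourable ethics opinion and authority approval before it is implemented.

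### When a second non-fatal DLT closes a verification level, the visible text has no rule for DLT-free patients already on it, and Section 8 bars lowering their dose

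*Combined protocol and SAP*

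**What the plan says.** Verification patients enter one after another. Section 10 sets the spacing: "thus a patient has to tolerate the first cycle (5 days) and the rest period of 16 days without DLT" before the next is added. A new patient can therefore start every 5 + 16 = 21 days while earlier DLT-free patients carry on with cycles at the same level.

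For a second DLT, Sections 9 and 10 say nearly the same thing: "patient accrual to this verification group is stopped with this second patient with DLT and de-escalation by a" 0.5 mg/m²/day step. The lower dose goes to further patients. The text summary in Section 10 follows the same path. None of the three mentions patients already on the level.

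Other provisions bear on those patients:

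- **Section 7.4:** "Treatment with tTF-NGR may continue until one of the following criteria applies". The criteria (progression, intercurrent illness, DLT, withdrawal, unfitness, loss to follow-up, death) all concern the individual patient.
- **Section 10, if every patient has had at least two cycles without a further DLT:** one patient may resume escalation, and "The remaining patients in the verification group will be further treated at this dose-level until any of the criteria under 7.4 is reached". If a DLT then occurs in cycle 3 or later, "this will be counted as DLT with all consequences, although the procedure of the study was not influenced before such an event occurred".
- **Section 8, on dose:** "De-escalation in individual patients in dosing is not allowed during the Study Period to not interfere with the description of Dose Limiting Toxicity (DLT"). The same sentence names the MTD.
- **Section 8, on timing:** "Delays in dosing of the next application for up to 6 days in individual patients are allowed in case anticipated adverse events". These are events that need to be dealt with before dosing goes on, such as platelet drops or infusional reactions.
- **Section 10, fatal DLT only:** "In the unlikely event that further patients are treated with this dose, treatment in these patients will be stopped at this dose level". Their further treatment is left to the investigator.

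**The concern.** Two patients with DLT out of six is the plan's own criterion for a dose above the MTD. At the moment that criterion is met, the text redirects only future patients. Those already on the level may go on receiving a drug whose anticipated toxicities, listed in Section 7.1, include arterial occlusion, embolism and DIC.

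The natural safer course, one dose step down, is closed by Section 8. Its stated reason is to keep the description of DLT and MTD clean, but for the closed level that question has just been settled. The result is uneven in two ways. A fatal DLT protects the other patients at that dose, whereas two non-fatal DLTs do not. And under Section 10 a patient whose own DLT has resolved, with stable disease or response, may be treated off study at a tolerated dose, whereas a DLT-free patient on study may not be lowered.

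A late DLT raises a further question. By then one patient may have escalated above the level, and the text does not say whether that patient must stop.

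**Working it through.** **The plan's own figure.** Section 16.1 gives a minimum of 7 patients: 1 escalation patient with DLT + 1 verification patient with the second DLT + 5 patients one step lower = 7. This reproduces. On that path the second DLT is in the first verification patient, so no DLT-free verification patient is left on the closed level.

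**How many patients can be affected.** If the second DLT falls in the first cycle of verification patient k (k = 1 to 5), up to k − 1 DLT-free patients are on the level: 0, 1, 2, 3 or 4.

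**How often.** The documents give no DLT probability, so p per patient is assumed, equal and independent. The probability that the second DLT is in patient k is (1 − p)^(k−1) × p. The probability that the level closes is 1 − (1 − p)^5. Given closure, the probability that at least one DLT-free patient was enrolled earlier is 1 − p / [1 − (1 − p)^5].

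| p | P(closure) | P(at least one, given closure) | Mean number, given closure |
|---|---|---|---|
| 0.10 | 0.410 | 0.76 | 1.79 |
| 0.20 | 0.672 | 0.70 | 1.56 |
| 0.33 | 0.865 | 0.62 | 1.25 |
| 0.50 | 0.969 | 0.48 | 0.84 |

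These are upper figures, because some of those patients may already have left for progression.

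**How much further treatment (illustration).** Assume starts on days 0, 21, 42, 63 and 84, cycles every 21 days, no progression, and dosing throughout the Study Period window of Section 7.4. With 3 months taken as 91 days, that window ends at start + 4 + 91 = start + 95 days. Cycles then begin at start + 0, 21, 42, 63 and 84, so each patient has five. Infusions on the day of the DLT are taken as already given.

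| Second DLT, first day of cycle 1 of patient | Full further cycles in the others | Infusions left in current cycles | Total infusions |
|---|---|---|---|
| 1 (day 0) | 0 | 0 | 0 |
| 2 (day 21) | 3 | 4 | 3 × 5 + 4 = 19 |
| 3 (day 42) | 2 + 3 = 5 | 8 | 25 + 8 = 33 |
| 4 (day 63) | 1 + 2 + 3 = 6 | 12 | 30 + 12 = 42 |
| 5 (day 84) | 0 + 1 + 2 + 3 = 6 | 16 | 30 + 16 = 46 |

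Section 6.1 asks for a life expectancy of only 6 weeks, so shorter stays are likely. With the second DLT in patient 5's first cycle and stays of 2, 3, 4 or 5 cycles, the full further cycles across all patients are 0, 1, 3 or 6. In the other direction, Section 17 describes the three months as follow-up. On that reading the Study Period sets no five-cycle cap.

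**Late DLT.** Patient 5 completes two cycles on day 84 + 42 = 126. That is the earliest day on which the continuation sentence in Section 10 applies and escalation can resume. A DLT in patient 5's third cycle (days 126 to 146) could bring the level to 2/6 while another patient is already at d1 + 0.5 mg/m²/day.

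**The case against.** The strongest reply is that these patients are not unprotected. By the CTCAE definitions in Section 9, Grade 3 includes events for which hospitalisation is indicated and Grade 4 is life-threatening. Most second DLTs would therefore be SAEs, reported within 24 hours (13.2) and reviewed for whether trial conduct should change (13.3). The study calendar has eligibility checked before each cycle and weekly. Section 17 lets the investigator remove a patient whose health is at risk, Section 22 allows immediate-hazard changes, and the DSMB advises (12.4.1). Section 7.4 is permissive, so stopping a patient needs no amendment.

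All of this stands. A reader might infer that a second DLT triggers no safeguard, or that the plan obliges patients to stay on a closed level. The documents support neither. The direction to treat further is conditional on no further DLT over two cycles in every patient, and becomes a problem only if a late DLT follows. What survives is narrower: no safeguard prescribes a hold or an outcome for these patients, and a laboratory-only DLT that is not an SAE could miss the SAE review.

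It can also be said that continuing is defensible. In the first-cycle scenarios each DLT-free patient has already tolerated at least one full cycle and rest at the dose, and a cohort classification does not prove individual intolerance. That is a legitimate choice, but the text does not state it, and Section 8 still removes the intermediate option.

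Finally, Section 9 refers to a scheme, and the figures in Sections 9 and 10 are not shown. One of them might settle the point.

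**Conclusion.** The gap holds for the visible text. After a second non-fatal DLT, DLT-free patients already on the level (up to four for a first-cycle DLT, none on the seven-patient path) have no stated rule. Section 7.4 permits continuation and Section 8 bars a lower dose during the Study Period. The plan already recognises the need in the fatal case, so this is worth correcting rather than a matter of taste.

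The size is uncertain: from no full further cycle to several per patient. The infusion totals are illustrations under an assumed calendar. A reader might take 46 as an expected value or a firm ceiling. It is neither, since it needs no progression, a DLT on one particular day and one reading of the three-month window. Nor should the point be read as an error in dose-finding: the MTD rule and the minimum of 7 are unaffected.

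**What to change.** **Section 10.** Extend the fatal-DLT stop-and-decide sentence to the second DLT at any level, whether it arises in the first two cycles or later. Current patients at or above that level, including one already escalated, receive no further infusion there until the investigator has completed a prompt, documented review.

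**Section 8.** Add an exception: after that review, DLT-free patients may continue one step (0.5 mg/m²/day) below the closed level. Do not count them in the lower level's six-patient MTD cohort, which preserves the purpose of the bar. The option should remain permissive, because the lower level has not yet been cleared in six patients and may itself be de-escalated.

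**Cost.** Protocol wording only. Some tolerating patients will have a cycle interrupted or a dose reduced, and some follow-up at the closed level is lost. On the illustrative calendar, a DLT in patient 5 on day 84, 85, 86 or 87 interrupts 16, 12, 8 or 4 infusions across four patients. From day 88 nobody is mid-cycle, and at most 105 − 88 = 17 days remain for the review before the next cycle starts.
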